8. ETHICAL AND REGULATORY REQUIREMENTS

8.1 Ethical conduct of the study

The study will be performed in accordance with ethical principles that have their origin in the Declaration of Helsinki and are consistent with ICH/Good Clinical Practice, applicable regulatory requirements and the AstraZeneca policy on Bioethics and Human Biological Samples.

8.2 Patient data protection

The Informed Consent Form will incorporate (or, in some cases, be accompanied by a separate document incorporating) wording that complies with relevant data protection and privacy legislation.

AstraZeneca will not provide individual genotype results to patients, any insurance company, any employer, their family members, general physician or any other third party, unless required to do so by law.

Extra precautions are taken to preserve confidentiality and prevent genetic data being linked to the identity of the patient. In exceptional circumstances, however, certain individuals might see both the genetic data and the personal identifiers of a patient. For example, in the case of a medical emergency, a study medical representative or an investigator might know a patient's identity and also have access to his or her genetic data. Also Regulatory authorities may require access to the relevant files, though the patient's medical information and the genetic files would remain physically separate.

The exception to the above is the result of the Myriad *gBRCA* test. This will be made available to the Investigator and patient.

8.3 Ethics and regulatory review

An IRB must approve the final study protocol, including the final version of the Informed Consent Form and any other written information and/or materials to be provided to the patients. The investigator will ensure the distribution of these documents to the applicable IRB, and to the study site staff.

The opinion of the IRB should be given in writing. The investigator should submit the written approval to the CTSU before enrolment of any patient into the study.

The IRB should approve all advertising used to recruit patients for the study.

AstraZeneca/BIG/Partners (and NRG Oncology/CTEP for US centres) should approve major modifications to the Informed Consent Form that are needed to meet local requirements.

If required by local regulations, the protocol should be re-approved by the IRB annually.

Before enrolment of any patient into the study, the final study protocol, including the final version of the Informed Consent Form must be approved by a local IRB or the NCI Central Institutional Review Board (CIRB), according to local regulations.

NRG Oncology will handle the distribution of these documents to the national regulatory authorities.

AstraZeneca/BIG/Partners will provide Regulatory Authorities, IRBs/Ethics Committees and Principal Investigators with safety updates/reports according to local requirements, including SUSARs (Suspected Unexpected Serious Adverse Reactions), outside the United States, where relevant. NRG Oncology will determine distribution of safety updates/reports as appropriate, in the United States.

Each Principal Investigator is responsible for providing the IRB with reports of any serious and unexpected adverse drug reactions from any other study conducted with the investigational product according to local requirements. If applicable, AstraZeneca will provide this information to the Principal Investigator so that he/she can meet these reporting requirements.

8.4 Informed consent

The Principal Investigator(s) at each centre will:

- Ensure each patient is given full and adequate oral and written information about the nature, purpose, possible risk and benefit of the study
- Ensure each patient is notified that they are free to discontinue from the study at any time
- Ensure that each patient is given the opportunity to ask questions and allowed time to consider the information provided

- Ensure each patient provides signed and dated informed consent before conducting any procedure specifically for the study
- Ensure the original, signed Informed Consent Form(s) is/are stored in the Investigator's Study File
- Ensure a copy of the signed Informed Consent Form is given to the patient
- Ensure that any provisions for patients harmed as a consequence of study participation are described in the informed consent form that is approved by an IRB.

8.5 Changes to the protocol and informed consent form

Study procedures will not be changed without the mutual agreement of the International co-ordinating Investigator, National Co-ordinating Investigator, and the Principal Investigator and AstraZeneca/BIG/NRG Oncology/Partners and the study Steering Committee.

If there are any substantial changes to the study protocol, then these changes will be documented in a study protocol amendment and where required in a new version of the study protocol (Revised Clinical Study Protocol).

Any protocol amendment must be approved by the relevant IRB and if applicable, should obtain the national regulatory authority approval, before implementation. Local requirements are to be followed for amended protocols.

NRG Oncology will distribute any subsequent amendments and new versions of the protocol to each Principal Investigator(s). For distribution to IRBs see [Section 8.3](#).

If a protocol amendment requires a change to a centre's Informed Consent Form, AstraZeneca/BIG/Partners, NRG Oncology/CTEP for US centres, and the centre's IRB are to approve the revised Informed Consent Form before the revised form is used.

If required by local regulations, any administrative changes will be communicated to or approved by each IRB.

8.6 Audits and inspections

Authorised representatives of NRG Oncology may perform audits or inspections at the centre, including source data verification. The purpose of an audit or inspection is to systematically and independently examine all study-related activities and documents, to determine whether these activities were conducted, and data were recorded, analysed, and accurately reported according to the protocol, Good Clinical Practice (GCP), guidelines of the International Conference on Harmonisation (ICH), and any applicable regulatory requirements. The investigator/site staff should contact the Protocol Officer immediately if contacted by a regulatory agency about an inspection at the centre.

9. STUDY MANAGEMENT

9.1 Pre-study activities

Qualification visits are not performed by NRG Oncology. NRG Oncology Member Institutions must determine that the sites are appropriate for the study. NRG Oncology distributes the approved protocol to its member institutions which are in good standing. Those sites which are confident that they have significant investigator interest and available patients proceed by seeking local (or central) Institutional Review Board approval. Upon receipt of the approval, a database of site IRB approvals is maintained through the NCI CTSU. Patient entry cannot proceed unless an up-to-date IRB approval is in this database.

9.2 Training of study site personnel

The Principal Investigator should ensure that appropriate training relevant to the study is given to all site staff, and that any new information relevant to the performance of this study is forwarded to the staff involved.

The Principal Investigator will maintain a record of all individuals involved in the study (medical, nursing and other staff).

9.3 Monitoring of the study

The study will be monitored by site audit visits, submission of copies of source documents for centralized review, and communication with the investigator and appropriate staff by NRG Oncology to:

- Provide information and support to the investigator(s)
- Confirm that facilities remain acceptable
- Confirm that the investigational team is adhering to the protocol, that data are being accurately and timely recorded in the eCRFs, that biological samples are handled in accordance with the B-55/6-13 Pathology and Correlative Science Instructions and that study drug accountability checks are being performed
- Perform source data verification (a comparison of the data in the eCRFs with the patient's medical records at the hospital or practice, and other records relevant to the study) including verification that the appropriate version of the consent form was used and that it was signed and dated prior to any study procedures. This will require direct access to all original records for each patient (e.g. clinic charts)
- If relevant, ensure withdrawal of informed consent to the use of the patient's biological samples is reported and biological samples are identified and disposed of/destroyed accordingly, and the action is documented, and reported to the patient.

The investigator will provide direct access to source data/documents for audits, IRB review, and regulatory inspections. NRG Oncology will be available between visits if the investigator(s) or other staff at the centre needs information and advice about the study conduct.

9.4 Study timetable and end of study

The end of the study is defined as ‘the last visit of the last patient undergoing the study’.

The study is expected to start in Q1 2014 and to end by 2028.

The study will end approximately 10 years following the randomisation of the last patient. Patients will be followed up until 10 years after the randomisation of the last patient.

The study may be prematurely terminated at individual centres if the study procedures are not being performed according to GCP, or if recruitment is slow. AstraZeneca may also terminate the entire study prematurely upon recommendations of the study IDMC if concerns for safety arise within this study or in any other study with olaparib.

10. DATA MANAGEMENT

Data management will be performed by the NRG Oncology SDMC.

The data collected through third party sources will be obtained and reconciled against study data by Frontier Science.

Adverse events and medical/surgical history will be classified according to the terminology of the latest version of the Medical Dictionary for Regulatory Activities (MedDRA). Medications will be classified according to the AstraZeneca Drug Dictionary. Coding will be done by Frontier Science.

Additional details of data management procedures can be found in the Data Management Plan for the Study. This document will be continuously updated through the life of the study.

Data queries will be raised for inconsistent, impossible or missing data. All entries to the study database will be available in an audit trail.

The data will be validated as defined in the Data Management Plan. Quality control procedures will be applied to each stage of data handling to ensure that all data are reliable and have been processed correctly. The Data Management Plan will also document the roles and responsibilities of the various functions and personnel involved in the data management process.

When all data have been coded, validated, and locked, clean file will be declared. Any treatment revealing data may thereafter be added and the final database will be locked.

The results from genetic research may be reported in the CSR for the main study, or in a separate report as appropriate. Refer to [Appendix C](#).

11. EVALUATION AND CALCULATION OF VARIABLES

11.1 Calculation or derivation of efficacy variable(s)

11.1.1 Primary endpoint

The primary endpoint of the trial is invasive disease free survival (IDFS), defined as the time from randomisation to date of first recurrence, where recurrence is defined as loco-regional, distant recurrence, new cancer or death from any cause. IDFS is further detailed according to the standardised STEEP system definition ([Hudis et al 2007](#)) as one of the following:

- Ipsilateral invasive breast tumour recurrence (IIBTR): Invasive breast cancer involving the same breast parenchyma as the original primary.
- Regional invasive breast cancer recurrence: Invasive breast cancer in the axilla, regional lymph nodes, chest wall, and skin of the ipsilateral breast.
- Distant recurrence: Metastatic disease-breast cancer that has either been biopsy confirmed or radiologically diagnosed as recurrent invasive breast cancer.
- Death attributable to any cause, including breast cancer, non-breast cancer, or unknown cause.
- Contralateral invasive breast cancer.
- Second primary non-breast invasive malignancies (i.e., excluding new in situ carcinomas of any site). Second primary non-breast invasive malignancies include hematologic malignancies and MDS. Squamous or basal cell skin cancers will not be counted as primary endpoint events.

Loco-regional recurrence of the disease (ipsilateral or regional invasive breast cancer) should be cytologically/histologically confirmed. Appropriate imaging (CT, MRI bone and/or PET scan) of the chest/abdomen/pelvis or any other area as clinically indicated should be performed at the time of local recurrence to exclude further spread of the disease. Distant recurrence should be diagnosed by radiological examination and/or histopathological confirmation when metastatic lesion is easily accessible for biopsy.

For confirmed local recurrence events, the earliest date of diagnosis based on an objective finding (physical exam, radiological/imaging assessment, cytological/histopathological assessment) will be used to determine the time to event for the analysis but not the date of the first symptoms or blood analysis abnormality. For example if a physical exam results in 'suspected' disease recurrence and disease recurrence is then confirmed by cytology/histology then the date of the physical exam will be used to derive the time to event.

For confirmed distant recurrence the date of the earliest radiological/imaging examination or cytological/histopathological assessment linked to the diagnosis will be used to determine the time to event for the analysis (i.e. physical exam will not be considered within the derivation of time to distant recurrence nor will be symptoms or blood analysis).

Invasive contralateral breast cancer or invasive non-breast secondary primary cancer should be confirmed by histopathological report. The date of the earliest objective finding related to diagnosis of the new cancer will be used as the date of new cancer for the analysis.

If two recurrence events (local and distant) are reported within 2 months of each other then this is referred to as a simultaneous event and will be considered as a single event. In this situation the worst case will be taken as the event 'type' but the date of recurrence will be the earliest date of the two events. For example if local and distant recurrence are reported within a 2 month period then for the analysis and reporting of IDFS the event type will be distant recurrence but the date of recurrence will be the earliest date of the two events.

If two recurrence events are reported but more than 2 months has elapsed between the events then the events will be regarded as two separate recurrence events and the earliest event and corresponding date of event will be used in the derivation of IDFS (i.e. IDFS is based on the first recurrence event).

If a patient dies during the study with no documented disease recurrence or invasive contralateral breast cancer or invasive non-breast secondary primary cancer then death will be regarded as an event and the date of death will be used to determine the patients IDFS time.

Patients who have not had a recorded IDFS event at the time of the analysis will be censored at the date of their last disease evaluation. Disease evaluation includes mammogram and/or breast MRI (MRI preferred for patients younger than 50 years), other radiological/imaging examination or clinical examination (e.g. physical exam).

11.1.2 Secondary endpoints

11.1.2.1 Overall Survival

Overall survival is defined as the time from the date of randomisation until death due to any cause. Any patient not known to have died at the time of analysis will be censored based on the last recorded date on which the patient was known to be alive.

11.1.2.2 Distant disease free survival (DDFS)

DDFS will be defined as the time from randomisation until documented evidence of first distant recurrence of breast cancer. Distant recurrence will include the following events:

- Distant recurrence: Metastatic disease-breast cancer that has either been biopsy confirmed or radiologically diagnosed as recurrent invasive breast cancer.
- Death attributable to any cause, including breast cancer, non-breast cancer, or unknown cause.
- Second primary non-breast invasive cancer.

Evidence of distant recurrence should be provided by either radiological examination or preferably by histopathological examination when metastasis is easily accessible for biopsy.

Second primary non-breast invasive cancer should be confirmed by histopathological report.

For the analysis of DDFS, the date of the confirmed DDFS event will use the earliest assessment date from the radiological and/or histological or cytological assessment. For example if a patient has distant recurrence suspected by radiological examination which is later confirmed by biopsy then the date of the radiological examination will be used as the date of event.

Patients who do not have documented evidence of DDFS at the time of the analysis of DDFS will be censored at the date of their last clinical examination (i.e. last physical exam or radiological evaluation).

The first site of distant recurrence will be recorded and used in the analysis. Information on subsequent sites of recurrence will also be collected during follow-up assessments to ensure as complete as possible information on distant recurrence is obtained.

11.1.2.3 Incidence of contralateral invasive breast cancer, contralateral non-invasive breast cancer, new primary ovarian cancer, new primary fallopian tube cancer and new primary peritoneal cancer

The incidence of contralateral invasive breast cancer, contralateral non-invasive breast cancer, new primary ovarian cancer, new primary fallopian tube cancer and new primary peritoneal cancer will each be considered separately and be defined as the number and percentage of patients with documented evidence of contralateral invasive breast cancer, contralateral non-invasive breast cancer, new primary ovarian cancer, new primary fallopian tube cancer and new primary peritoneal cancer regardless of when this occurs (i.e. does not need to be their first recurrence event).

All patients should be followed for evidence of new primary breast cancers and all other cancers. This includes patients with a first event of local or distant recurrence as they may go on to develop new cancers in the future. All new cancers will be collected for all patients not just the first new cancer.

Data analyses of new contralateral breast cancer (invasive and non-invasive) will exclude patients who have had bilateral mastectomy prior to randomisation.

Data analyses of new ovarian cancers will exclude patients who have had both ovaries removed prior to randomisation.

Data analyses of new fallopian tube cancers will exclude patients who have had both fallopian tubes removed prior to randomisation.

Data analyses of new peritoneal cancer will include all patients in the ITT populations.

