- e All ongoing AEs/SAEs and any new AEs/SAEs identified during the 30 calendar days follow-up period after last dose of study medication must be followed to resolution unless the event is considered by the investigator to be unlikely to resolve, or the patient is lost to follow-up or in survival follow-up. If an investigator learns of any SAEs, including death, at any time after a patient has completed the 30 days post treatment follow-up period, and he/she considers there is a reasonable possibility that the event is causally related to the study treatment, the investigator should report it according to SAE reporting procedures for this study. Any cases of MDS/AML, any new second primary malignancies or diagnoses of pneumonitis occurring after the 30-day follow-up period should be reported as a SAE, regardless of investigator's assessment of causality, knowledge of the treatment arm, and irrespective of the timing of the event in relation to study therapy. Non-melanoma invasive skin cancers and all cases of carcinoma in situ need to be reported as a non-serious AE unless at least one of the seriousness criteria is met which then requires reporting as a SAE, see [Section 6.4.6](#). If a patient develops MDS/AML full diagnostic details and classification should be provided e.g. bone marrow and cytogenetic analysis reports, see [Sections 5.5.12.4](#) and [6.4.11.5](#). A questionnaire will be sent to any investigators reporting MDS/AML or new primary malignancies as an aid to provide detailed information on the case.

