12.2.5 Multiplicity strategy for primary and key secondary endpoints

[figure not shown]
The primary endpoint of the study is IDFS. However, key secondary endpoints will be OS and DDFS.

In order to describe the nature of the benefits of olaparib treatment IDFS, DDFS and OS will be tested at a 2-sided significance level of 5%.

However, in addition, in order to strongly control the overall type I error at 2.5% 1-sided, a multiple testing procedure (MTP) will be employed across the primary endpoint and all key secondary endpoints intended for label claims (DDFS and OS). The MTP will account for any interim analyses on IDFS, DDFS and OS and also planned further analyses post the primary IDFS analysis data cut off.

A hierarchical testing strategy will be employed where IDFS is tested first using the full test mass (i.e. full 2.5%, 1-sided alpha), then DDFS and OS will be tested if IDFS is significant based on a weighted proportion of the test mass (2% for DDFS and 0.5% for OS, 1-sided) which can be recycled to secondary endpoints not yet rejected. Testing stops when the entire test mass is allocated to non-rejected endpoints.

Figure 3 Multiple testing procedure

IDFS is planned to be analysed at the interim and the final analysis (see [Section 12.2.6](#) for further details). If IDFS is significant at the interim based on the ITT population then secondary endpoints will be formally tested at the interim based on the MTP outlined above. To account for multiple analyses on each endpoint a separate alpha spending function will be applied to each

endpoint ([Glimm et al 2010](#)). Further analyses of DDFS and OS with more mature follow up may be required for which some alpha will be reserved for significance testing.

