12.2.7 Sample size justification

The primary endpoint of the study is IDFS and patients will be randomised 1:1 to either olaparib 300 mg b.i.d. (twice daily) or matching placebo.

A total of 1800 patients will be randomised into the study to achieve 330 IDFS events. If the true HR for the comparison of olaparib versus placebo in terms of IDFS is 0.7 then with 330 events, the analysis of IDFS will have 90% power to demonstrate a statistically significant difference in IDFS, assuming a 2-sided 5% significance level. The critical HR value at the primary analysis is 0.805.

The actual accrual pattern between June 2014 and February 2018 is shown in [Table 16](#).

It is estimated that 1800 patients will be randomised by April/May 2019 so that the study will take approximately 5 years to complete recruitment (approximately 230 patients in US and approximately 1570 patients in the Rest of the World countries).

Table 16 Actual accrual between June 2014 and February 2018

Interval since start of randomisation (months)	Number of patients randomized in interval	Cumulative number of patients randomized	Average number of patients randomized per month in interval
0-6	21	21	3.5
6-12	94	115	15.7
12-18	174	289	29
18-24	180	469	33
24-30	229	698	38.2
30-36	249	947	41.5
36-42	234	1181	39
42-45*	118	1299	39.3

*Note: 3-month interval: December 2017 to February 2018 inclusive.

The primary analysis population will be all patients randomised (ITT). A subgroup analysis based on prior chemotherapy (adjuvant or neoadjuvant), prior platinum therapy (yes or no) and hormone receptor status (ER and/or PgR positive/HER2 negative versus TNBC) will be conducted to check for consistency in the treatment effect but this analysis is considered supportive of the primary analysis in the overall population.

During the trial, the Steering Committee will monitor the recruited patient population and actual event rate whilst remaining blinded to treatment. If the data suggests that the original sample size assumptions are incorrect such that achieving the required number of events with the current number of patients does not seem feasible then in consultation with the IDMC a decision may be made to increase the number of patients recruited into the trial to achieve the required 330 events.

12.2.8 Issues relating to racial and ethnic differences in the U.S.

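### As worded, a squamous or basal cell skin cancer counts as a DDFS event although it is excluded from IDFS

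*Protocol*

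**What the plan says.** Section 11.1.1 defines the IDFS component for second primary non-breast invasive malignancies with three rules:

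- New in situ carcinomas are out.
- "Second primary non-breast invasive malignancies include hematologic malignancies and MDS".
- "Squamous or basal cell skin cancers will not be counted as primary endpoint events".

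Section 1.3 repeats the same rules.

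Section 11.1.2.2 gives DDFS its own event list of three items: distant recurrence, death from any cause, and "Second primary non-breast invasive cancer". It adds one condition to the last item: "Second primary non-breast invasive cancer should be confirmed by histopathological report". It carries no skin-cancer exclusion, does not mention haematologic malignancy or MDS, and does not refer back to 11.1.1.

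Section 12.2.5 makes DDFS a key secondary endpoint intended for a label claim, inside the multiple testing procedure, with 2% 1-sided alpha. Table 15 in section 12.2.6 shows this as 4% 2-sided.

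**The concern.** DDFS is meant to support IDFS (section 1.3). Apart from the loco-regional and contralateral breast events that a distant endpoint leaves out by design, one would expect the two endpoints to count the same things. Here the exclusion of a common and usually curable type of cancer is tied in words to the primary endpoint and does not reach DDFS.

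A programmer who follows 11.1.2.2 would set a DDFS event at the date of a basal cell carcinoma in a patient who remains event-free for IDFS. Because DDFS takes the first event, a true distant relapse in that patient two years later would not enter the analysis. The result is a weaker and less interpretable test of the endpoint that carries most of the secondary alpha.

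**Working it through.** **1. The plan's own figures.** Section 12.2.7 states that "with 330 events, the analysis of IDFS will have 90% power to demonstrate a statistically significant difference in IDFS" at HR 0.7, 2-sided 5%, 1:1. By Schoenfeld's formula, events = 4(1.960 + 1.282)² / (ln 0.7)² ≈ 331, and power with 330 events is 0.8997. The figure reproduces. The DDFS alpha is 2 × 2% = 4% 2-sided, matching Table 15. No stated number is in dispute; the point concerns the event definition.

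**2. The two definitions side by side.**

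| Finding after randomisation | IDFS (11.1.1) | DDFS (11.1.2.2), as worded |
|---|---|---|
| In situ carcinoma | Excluded explicitly | Not an event, because the item says invasive |
| Squamous or basal cell skin cancer | Excluded explicitly | Event, if invasive and histologically confirmed |
| Haematologic malignancy, MDS | Included explicitly | Not mentioned |

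**3. Does the literal reading reach these skin cancers?** The protocol's own vocabulary says so. Table 3, footnote e (section 3.1) states: "Non-melanoma invasive skin cancers and all cases of carcinoma in situ need to be reported as a non-serious AE", unless a seriousness criterion is met. Section 6.4.9 uses the same term. A tumour the protocol calls invasive, outside the breast and newly arisen, fits the DDFS item.

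**4. Size.** The protocol states no DDFS event count and no DDFS effect size, so what follows is illustration.

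Possible numbers of skin cancers:
- Section 1.4 reports new primary malignancies other than MDS/AML in 22 of 3862 olaparib-treated patients (0.57%). Applied to 1800 patients, that is about 10 of all types; skin cancers are only some of them. I use 5 to 10 as the low range.
- Section 1.4 also cites skin-cancer rates of 1.6% (*BRCA1*) and 3.0% (*BRCA2*). Applied to 1800, these give 28.8 to 54, so 29 to 54. I treat this as an upper bound: neither the type of skin cancer nor the time frame is given, and not every case would be a first event.

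Model: D true DDFS events at HR 0.70 split as D/1.7 on placebo and 0.7D/1.7 on olaparib. Add k skin cancers, neutral between arms, k/2 to each:

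HR = (0.7D/1.7 + k/2) / (D/1.7 + k/2).

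For D = 250 the split is 147.06 and 102.94. Then k = 10 gives 107.94/152.06 = 0.710, and k = 54 gives 129.94/174.06 = 0.747.

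Power is by Schoenfeld with D + k events at 2-sided 0.02, the DDFS level at the final IDFS analysis in Table 15 without recycling, treated as a single look.

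| k | D = 200: HR, power | D = 250: HR, power | D = 300: HR, power |
|---|---|---|---|
| 0 | 0.700, 57.8% | 0.700, 68.9% | 0.700, 77.7% |
| 5 | 0.706, 56.5% | 0.705, 67.9% | 0.704, 76.9% |
| 10 | 0.712, 55.3% | 0.710, 66.9% | 0.708, 76.1% |
| 29 | 0.733, 51.0% | 0.727, 63.2% | 0.723, 73.2% |
| 54 | 0.756, 46.1% | 0.747, 58.8% | 0.740, 69.5% |

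The loss of power is about 1 to 2.5 points for 5 to 10 added events, and about 5 to 12 points for 29 to 54.

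**The case against.** The best reply is that 11.1.2.2 is shorthand. Elsewhere the protocol sets these skin cancers apart from second primaries without any tie to the primary endpoint: section 5.5.12.1 does so for stopping study drug, and section 6.4.9 for late SAE reporting. Section 6.4.9 also calls new primary cancers IDFS events without repeating the exclusions, so the authors do abbreviate. This makes it likely that the same category was intended for DDFS. It does not settle the matter, because those sections govern treatment and safety reporting, whereas 11.1.2.2 derives the endpoint and gives a complete event list.

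It is also fair to say that neutral events make the test conservative, that DDFS already counts deaths from any cause and other second primaries, and that the protocol nowhere promises that every DDFS event is an IDFS event. All of that stands and limits the severity.

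A reader might infer that MDS is left out of DDFS, so that a possible olaparib harm is treated differently in two linked endpoints. The documents do not support this. The inclusion sentence in 11.1.1 defines the category and, unlike the skin-cancer sentence, is not confined to the primary endpoint. The event-dating rules in 11.1.1 use a similar short form for IDFS itself, where MDS plainly counts. DDFS is silent on MDS, which is a reason to make the wording consistent but not evidence of an exclusion.

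**Conclusion.** The mismatch on squamous and basal cell skin cancers is real in the text and should be corrected. Followed literally, it lets DDFS fail before IDFS, displaces later distant relapses and dilutes a label-claim endpoint. It does not affect type I error or any stated alpha, event number or power.

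With a handful of skin cancers the effect is small: an HR of about 0.705 to 0.71 instead of 0.70, on an assumed 250 DDFS events. At the upper bound it is about 0.73 to 0.75. These figures rest on the assumed DDFS event count, on HR 0.70 carrying over from IDFS, and on skin cancers being neutral between arms.

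A reader might take the 1.6% and 3.0% rates as a forecast of 29 to 54 unwanted events, or conclude that a substantial share of DDFS events would be skin cancers. The protocol does not support either: the rates come from an outside study, with no time frame and no split by type, and there is no DDFS count to set them against. Severity is minor to moderate.

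**What to change.** In section 11.1.2.2, state that second primary non-breast invasive malignancies are defined for DDFS exactly as for IDFS in 11.1.1: in situ carcinomas and squamous or basal cell skin cancers do not count, and haematologic malignancies and MDS do. If a difference is intended, state it and give the reason. Carry the same sentence into the SAP if it is not already there.

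Make the change before any unblinded DDFS analysis, since altering the event list of a label-claim endpoint afterwards would look data-driven.

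The cost is one sentence. Section 11.1.2.3 already requires all new cancers to be collected for all patients, so no new data are needed. The only analytic consequence is that DDFS loses whatever skin-cancer events it would otherwise have counted.
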